8. STUDY PURPOSE AND ASSESSMENT

8.1 Study Purpose. The purpose of the proposed study is to evaluate safety of the iotaSOFT™ Insertion System when used by a surgeon to assist with inserting a cochlear implant electrode array. We will evaluate for successful device use during electrode array insertion via a surgeon questionnaire regarding device usability, monitor electrode array insertion time, assess CI electrode positioning or tip-fold-over by post-insertion X-ray, and measure electrode impedances and neural response telemetry at post-operative activation. A

set of relevant safety and effective use measures will be collected, and adverse events will be tracked and reported per applicable regulations.

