8.2 Study Assessments

8.2.1 Surgeon Questionnaire

Surgeon questionnaires will be administered to solicit information about device utility, ease of device use during the procedure, and clinical workflow in the surgical setting. The surgeon questionnaire shall not contain any subject data and therefore, does not impact subject safety, welfare or confidentiality. The questionnaire will be completed by the implanting surgeon following completion of the surgical procedure. The information will be gathered and tabulated for qualitative analysis. For more details, see the surgical questionnaire (FRM00002).

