Surgical insertion timing using the iotaSOFT™ insertion system will be evaluated via operative microscope video record analysis. Time stamp mark will start when the electrode begins insertion through appropriate cochlea opening (e.g. through round window or cochleostomy) and end when surgeon determines insertion is complete without further advancement as reviewed on operative microscope recording. The end time will be defined by when the electrode has been inserted fully or the surgeon stops electrode advancement. Should the insertion end due to unanticipated anatomical reasons or significant resistance in insertion, proper adverse event documentation will be completed.

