8.2.4 Post-Insertion Electrode Position X-ray Assessment

As per standard of care, following CI electrode array insertion, an intraoperative or post-operative “cochlea view” x-ray via c-arm will be performed to determine radiographically the insertion position of the electrode array and presence of tip-fold.

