10.8 Device Replacements

There is the possibility of device failures (e.g. the iotaSOFT drive unit does not move the electrode as intended, etc), in that case, the surgeon may troubleshoot per instructions for use (Attachment 8), ask for replacement sterile iotaSOFT drive unit, or abandon the study and revert to the standard manual insertion techniques to complete the CI insertion procedure. Such events should be documented.

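### Section 8.1 evaluates successful device use through the operating surgeon's usability questionnaire, which as described does not measure whether the device completed the insertion

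*Protocol*

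**What the plan says.** The aim in Protocol 8.1 is safety: "The purpose of the proposed study is to evaluate safety of the iotaSOFT™ Insertion System". The next sentence lists what will be assessed and gives each item its own instrument. For success of use it says: "We will evaluate for successful device use during electrode array insertion via a surgeon questionnaire regarding device usability". Insertion time, X-ray position or tip fold-over, and impedance and telemetry follow as separate items.

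Section 8.2.1 says the questionnaire is meant to "solicit information about device utility, ease of device use during the procedure, and clinical workflow in the surgical setting". On the respondent: "The questionnaire will be completed by the implanting surgeon following completion of the surgical procedure". On the analysis: "The information will be gathered and tabulated for qualitative analysis". It refers to form FRM00002 for details; that form is not among the documents.

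Three other sections bear on the point:

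- **8.2.2 (timing).** "Surgical insertion timing using the iotaSOFT™ insertion system will be evaluated via operative microscope video record analysis". Timing ends at full insertion or when the surgeon stops advancing the array.
- **8.2.4 (X-ray).** A cochlea-view image is taken "to determine radiographically the insertion position of the electrode array and presence of tip-fold".
- **10.8 (device failure).** The surgeon may troubleshoot, "ask for replacement sterile iotaSOFT drive unit", or abandon the study and finish by hand. Such events should be documented.

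**The concern.** Whether the device completed an insertion is an observable yes/no fact. Utility, ease and workflow are opinions about using it. The two can part company: a surgeon may find the system convenient in a case that ended by hand, or awkward in a case that it completed. The respondent is also the operator, in a single-arm, open-label study, so no comparison or independent reading offsets the opinion.

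At stake is the answer to one named outcome. Following 8.1 and 8.2.1 as written, the report on successful use would be a qualitative tabulation of views. The events that most plainly show unsuccessful use would sit in a separate record with no stated bearing on it.

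The denominator is also open. Section 10.8 treats reversion as abandoning the study and does not say whether such a case still counts.

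**Working it through.** The protocol gives no success rate, performance goal or sample-size basis for this outcome, so there is no figure to reproduce. The check is mainly a comparison of sections.

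**Step 1: what each source can show, as described.**

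| Source | What it records | Shows that the device completed the insertion? |
|---|---|---|
| Questionnaire (8.2.1) | Surgeon's view of utility, ease, workflow | No such item described |
| Microscope video (8.2.2) | Start and end of advancement | Largely, though used only for timing, and the end is partly the surgeon's decision |
| X-ray (8.2.4) | Array position, tip-fold | No; it cannot tell device from manual placement |
| Failure record (10.8) | Failure, replacement, reversion | Shows when it did not, but is not linked to the outcome |

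The only source that 8.1 assigns to success is the one that does not describe a completion item. The video and the failure record together supply what is missing.

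**Step 2: is success defined elsewhere?** No section defines successful use from the video, the X-ray or the failure record. The 8.1 purpose paragraph does promise a set of safety and effective-use measures, but it does not say which of them decides success.

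**Step 3: what the denominator can do (illustration).** Section 9.1 allows up to 30 subjects. Assume one insertion each, so n = 30; bilateral procedures, foreseen in 10.2, would change this. Let k be the number of attempted insertions that end in manual insertion. The documents give no value for k, so a range is shown. With all attempts counted, the rate is (30 − k)/30, with the Clopper-Pearson 95% interval. With converted cases dropped, it is (30 − k)/(30 − k) = 100%, with lower limit 0.025^(1/(30 − k)).

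| k (assumed) | All attempts counted | Converted cases dropped |
|---|---|---|
| 0 | 30/30 = 100% (88.4% to 100%) | 30/30 = 100% (88.4% to 100%) |
| 1 | 29/30 = 96.7% (82.8% to 99.9%) | 29/29 = 100% (88.1% to 100%) |
| 3 | 27/30 = 90.0% (73.5% to 97.9%) | 27/27 = 100% (87.2% to 100%) |
| 6 | 24/30 = 80.0% (61.4% to 92.3%) | 24/24 = 100% (85.8% to 100%) |

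Dropping converted cases returns 100% whatever k is, so the rate would then carry no information about conversion. The questionnaire, as described, would not reveal k either.

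**The case against.** The strongest reply is that little is lost. The study's purpose is safety, and successful use is one descriptive item in a small single-arm study. Conversions and replacements are to be documented under 10.8. Section 8.2.2 requires adverse event documentation when insertion ends because of unanticipated anatomy or significant resistance. Tip fold-over has its own X-ray assessment. How such events are counted commonly belongs in a statistical analysis plan, which is not shown, and FRM00002 may hold a completion item.

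Much of this stands, and it rules out stronger readings that a reader might infer:

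- That a fold-over or a conversion would go unrecorded. The protocol provides for recording both.
- That the X-ray and video already show success directly. The X-ray cannot separate device from manual placement, and the video end point rests partly on the surgeon's judgement.
- That the ratings would lean favourable. Nothing in the documents establishes this.
- That a second drive unit or a tip fold-over is a failure of use. Section 10.8 offers replacement as a response to device failure, and 4.2 lists fold-over as a known risk of manual insertion.
- That manual guidance is a failure. Section 10.4 makes guidance with standard instruments part of the described use.

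What the reply does not remove is that the protocol itself chose the instrument. An unspecified analysis could be left to a later plan. Here a named measure is attached to a named outcome, and as described it measures something else. A completion item on the form would narrow the gap, but it would still be the operator's own report and would not settle the denominator.

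**Conclusion.** The point holds, limited to the outcome of successful device use. Section 8.1 evaluates that outcome with a usability questionnaire that, as 8.2.1 describes it, does not measure whether the device completed the insertion. The failures and reversions documented under 10.8 are not tied to the outcome, and 10.8 leaves the place of converted cases unclear.

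No real magnitude can be given. In the illustration, 1 to 6 conversions among 30 attempts correspond to 96.7% down to 80.0% with all attempts counted, against 100% in every case with conversions dropped. Those counts, and one insertion per subject, are assumptions.

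A reader might go further and conclude that the trial cannot support any statement on successful use. The documents do not support that, because the video and failure record needed for such a statement are already planned. The conclusion also rests on 8.2.1 describing FRM00002 fairly. This should be changed before the data are summarised, but it does not undermine the study as a whole.

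**What to change.** Reword 8.1 so that successful device use is evaluated per insertion, as array advancement completed with the iotaSOFT system without reversion to manual insertion. Take it from the microscope video already reviewed under 8.2.2 and from the 10.8 failure and conversion record. Because the 8.2.2 end time covers both full insertion and a stop by the surgeon, record which of the two ended advancement.

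Report the count and percentage with an exact 95% interval over all insertions in which device use was attempted. State in 10.8 that converted cases stay in that denominator. Report drive-unit replacement, and X-ray position and tip fold-over, alongside as separate items. Keep the questionnaire as a description of usability only.

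The cost is protocol wording and a few check-boxes on the case report form. No procedure is added, since the video is already reviewed and the X-ray is standard of care. The downside for the sponsor is a success figure that may be lower than surgeon opinion suggests.

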8.2 Study Assessments

8.2.1 Surgeon Questionnaire

Surgeon questionnaires will be administered to solicit information about device utility, ease of device use during the procedure, and clinical workflow in the surgical setting. The surgeon questionnaire shall not contain any subject data and therefore, does not impact subject safety, welfare or confidentiality. The questionnaire will be completed by the implanting surgeon following completion of the surgical procedure. The information will be gathered and tabulated for qualitative analysis. For more details, see the surgical questionnaire (FRM00002).

8.2.2 Surgical Electrode Array Insertion Timing

iotaSOFT™ CI insertion system utilizes the same surgical approach and procedure as current manual CI insertion techniques without alteration to the approach workflow. The current standard CI surgical procedure includes a cortical mastoidectomy, facial recess approach to the cochlea, and placement of the CI receiver/stimulator under skin flap in bone recess. This is followed by preparation of the round window or cochleostomy and appropriate cochlea opening. Subsequent manual insertion of the electrode array is performed into the cochlea by grasping the electrode utilizing one or a combination of instruments or forceps. The surgeon then gently inserts the array by hand under direct microscope visualization for any buckling while avoiding excessive forces per universal insertion principles and specific CI manufacturer guidelines.¹⁷⁻²⁰ Following CI electrode array insertion, a small fascia graft or muscle plug is placed to seal the cochlea opening to secure the array and the excess electrode lead is additionally secured in the mastoid cavity.²⁰ The CI ground is then placed in soft tissues at the zygomatic root.

Using the iotaSOFT™ insertion system to assist with electrode array insertion, the surgeon will perform the above described standard surgical approach but will have more speed control of the electrode array insertion and stable trajectory as well as improved consistency of insertion. Should the surgeon need to quickly revert to alternative standard manual insertion techniques at any point during a CI procedure which utilizes the iotaSOFT™ insertion system, this can be accomplished immediately without the need to modify the surgical approach or perform additional surgical steps aside from uncoupling of the iotaSOFT drive head from the CI lead in seconds.

Surgical insertion timing using the iotaSOFT™ insertion system will be evaluated via operative microscope video record analysis. Time stamp mark will start when the electrode begins insertion through appropriate cochlea opening (e.g. through round window or cochleostomy) and end when surgeon determines insertion is complete without further advancement as reviewed on operative microscope recording. The end time will be defined by when the electrode has been inserted fully or the surgeon stops electrode advancement. Should the insertion end due to unanticipated anatomical reasons or significant resistance in insertion, proper adverse event documentation will be completed.

8.2.4 Post-Insertion Electrode Position X-ray Assessment

As per standard of care, following CI electrode array insertion, an intraoperative or post-operative “cochlea view” x-ray via c-arm will be performed to determine radiographically the insertion position of the electrode array and presence of tip-fold.

8.2.3 Post-Activation Impedance and Neural Telemetry

Per current standard of care, post-activation impedance and neural telemetry measurements will be collected at the initial in-clinic activation of the CI (approximately 2 weeks to 1 month following surgery), and at 1-month, 3-months, and 6 months post-activation using the standard non-invasive measurement techniques per CI manufacturer guidelines. Measurement values will be reported via case report form.

8.2.6 Safety Assessments

8.2.6.1 Adverse Events will be reported and documented throughout the duration of the study. All reported events will be recorded on case report forms and determinations will be made as to the whether the events are Adverse Events, Serious Adverse Events, Unanticipated Adverse Device Effects, and/or related to the investigational device or the procedure.

9. STUDY DESIGN

The study is a prospective, single arm, open-label study. Baseline medical data questionnaire will be collected for each subject prior to CI surgery. This will aid in determining adverse events as a result of the study. Aside from the insertion timing, data for evaluation of device safety will be collected after the device has been placed.

9.1 Number of Sites and Subjects

Up to 30 subjects will be enrolled at up to 3 investigational sites. Each site will have adequate facilities for all medical procedures, and sites selected will represent private and larger medical center practice settings. All sites will be required to receive Institutional Review Board (IRB) approval prior to study initiation. Should clearance of the marketing application be received during the study, the Sponsor will determine whether to continue enrolling new subjects. Subjects already enrolled in the study who have not been implanted will be allowed to continue in the study.

9.2 Cochlear Implant Electrodes

Only FDA approved cochlear implant electrode arrays and those validated for compatible use by the iotaSOFT manufacturer will be used for this study, specifically those without a sheath or stylet required for use including MedEl Flex, Cochlear 622/624, and AB Slim J electrode arrays.

9.3 Subject Selection and Withdrawal

Subjects will be screened to verify that they meet all inclusion and exclusion criteria prior to being enrolled in the study. Informed consent will be obtained from every subject as described in Section 13.2 before they are considered enrolled in the study.

9.4 Inclusion criteria

- 1) Candidate for cochlear implantation according to FDA indications for only the following

electrode arrays: **MedEl Flex, Cochlear 622/624, AB Slim J**

- 2) Age 18 years or older at the time of enrolment
- 3) Willingness to participate in and to comply with all requirements of the protocol
- 4) Fluent speaker of American English due to language used in consent document.

9.5 Exclusion criteria

The Subject must not have known or active medical issues that would preclude having a CI device, including:

- 1) Prior cochlear implantation in the ear to be implanted
- 2) Ossification or any other cochlear anomaly that might prevent complete insertion of the electrode array
- 3) Craniofacial abnormality or Abnormal cochlear/nerve anatomy on pre-operative CT or MRI imaging (excluding a mild Mondini malformation or Large Vestibular Aqueduct Syndrome)
- 4) Deafness due to lesions of the acoustic nerve or central auditory pathway
- 5) Diagnosis of auditory neuropathy
- 6) Active middle-ear infection
- 7) Additional handicaps that would prevent participation in evaluations
- 8) Unrealistic expectations on the part of the subject, regarding the possible benefits, risks and limitations that are inherent to the procedure and investigational device
- 9) Must not fit the definition of a vulnerable subject, as per FDA regulations 21 CFR Parts 50 and 56^{21,22}

10 DETAILED STUDY PROCEDURES

10.1 Candidacy and Enrolment

Once a subject has been determined a candidate for cochlear implantation according to FDA indications the patient will be invited to participate in this study. This will take place at the CI evaluation or the preoperative visit. The subject will be given the Informed Consent and given ample time to review and ask questions (see 13.2 for more information on the consent process). The subject will be given the medical health history questionnaire (FRM00001). Study enrolment will be accounted for on Attachment 6.

10.2 Surgical Preparation

Preparation for surgery will occur as per standard clinical procedures. Surgeons will be trained on iotaSOFT system use and operation with training certification by iotaSOFT manufacturer personnel prior to use, including at least a 1-hour period between training and use of the device. Training will be documented on Attachment 7. Operating room setup and procedure preparation will be followed according to the iotaSOFT™ insertion system instructions for use to ensure the sterile field is not compromised and system is operational (Attachment 8). The operative microscope will be capable of video recording collection. If bilateral cochlear implant

procedure, the first iotaSOFT drive unit will be discarded and new, sterile unit will be used for the contralateral electrode array insertion.

10.3 Surgeon Device Training

Surgeons will be trained on iotaSOFT system use and operation with training certification by iotaSOFT manufacturer personnel prior to use, including at least a 1-hour period between training and use of the device. Training will be documented on Attachment 7.

10.4 Device Surgical Use

CI surgery will be conducted as per each surgeon's standard clinical practice and surgical approach including cortical mastoidectomy and facial recess approach to the cochlea for cochlear implantation. The surgeon then secures the stage base to the skull at superior edge of mastoidectomy with two pre-loaded self-drilling cortical bone screws and supplied sterile screwdriver. The drive unit is placed into the stage base and the adjustable drive head is coupled to a compatible CI silicon lead by clapping clip action onto the CI excess silicone lead away from the electrode array. With manual surgeon manipulation, the drive unit head is positioned outside the facial recess and aligned to the surgeon-desired electrode array insertion trajectory. Before insertion begins, the surgeon selects the desired speed from 0.1mm/sec to 1.0mm/sec in 0.1mm/sec intervals using footpedal controller. With direct access and microscopic view of the surgical site, the surgeon advances or retracts the electrode array via footpedal while guiding the electrode array into the cochlea with standard manual CI instrumentation as necessary. Upon the completion of electrode array insertion and securing the array at the cochlea, the surgeon unclips the drive head and unit from the excess silicone lead then removes the device and screws from the patient for disposal. Per current standard of care, cochlea view X-rays will be performed, and the surgical site is then closed. For detailed device description and professional instructions for use see Attachment 1 & 8.

10.5 Subject Withdrawal or Early Termination

Subjects can choose to withdraw from the study at any time, for any reason, specified or unspecified, and without prejudice. Subjects will be withdrawn from the study for any of the following reasons: termination of study, request by the subject, development of an exclusion criterion prior to CI surgery (i.e., change in ability to meet protocol requirements).

10.6 Medications

No special medications are required for this study. Subjects will follow all standard clinical preparatory surgical procedures given to them by their doctor.

10.7 Protocol Deviations

A protocol deviation refers to a study-related activity that is not in compliance with the investigational protocol. Deviations that are required to protect the life or well-being of a subject do not require prior approval from the Sponsor and should be implemented immediately. The IRB and Sponsor must be notified within 5 (five) days of such an event.

If parts of the study are omitted or completed incorrectly, the event is to be noted on the Protocol Deviation Log provided to the Investigator in the study Regulatory Binder. Depending on the type or severity of the deviation the Investigator may be required to notify the IRB and/or Sponsor if the deviation impacts safety or performance of the subject or data integrity.

10.8 Device Replacements

There is the possibility of device failures (e.g. the iotaSOFT drive unit does not move the electrode as intended, etc), in that case, the surgeon may troubleshoot per instructions for use (Attachment 8), ask for replacement sterile iotaSOFT drive unit, or abandon the study and revert to the standard manual insertion techniques to complete the CI insertion procedure. Such events should be documented.

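### Section 10.8 can be read as ending study participation when the device fails, an exit that Section 10.5 does not recognise and that puts later safety data from converted subjects at risk

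*Protocol*

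**What the plan says.** Section 10.8 (Device Replacements) gives the surgeon three options when the device fails: troubleshoot, obtain a replacement sterile drive unit, or "abandon the study and revert to the standard manual insertion techniques to complete the CI insertion procedure". It adds that such events should be documented. It does not say what then happens to the subject.

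Section 10.5 lets subjects withdraw at any time and gives the reasons for which they will be withdrawn: "termination of study, request by the subject, development of an exclusion criterion prior to CI surgery".

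The study is a single-arm safety study. Section 8.1 also makes device performance a matter for evaluation: "We will evaluate for successful device use during electrode array insertion via a surgeon questionnaire regarding device usability".

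The data to be collected are set out in Section 8.2:
- Questionnaire (8.2.1): "The questionnaire will be completed by the implanting surgeon following completion of the surgical procedure".
- X-ray (8.2.4), taken "to determine radiographically the insertion position of the electrode array and presence of tip-fold".
- Impedance and neural telemetry (8.2.3), measured at activation ("approximately 2 weeks to 1 month following surgery), and at 1-month, 3-months, and 6 months post-activation").
- Safety (8.2.6): "Adverse Events will be reported and documented throughout the duration of the study".

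Section 10.7 covers departures from the plan: "If parts of the study are omitted or completed incorrectly, the event is to be noted on the Protocol Deviation Log".

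**The concern.** In a single-arm study of safety and successful device use, a device failure is itself a result. A rule that releases a subject from the study because of that failure makes the completeness of follow-up depend on the outcome. A site following 10.8 to the letter could stop reporting adverse events and stop transferring the scheduled measurements in exactly the subjects whose device failed.

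Those subjects matter for a further reason. Section 5.1 argues that patient risk does not exceed standard care partly because the surgeon can revert to manual insertion at once. Converted subjects are the ones whose later course bears most directly on that argument.

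Who remains under data collection is for the protocol to settle. An analysis plan can decide how to count a subject, but it cannot recover adverse events that were never reported.

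**Working it through.** The protocol states no figure on this point, so there is none to reproduce. The check compares the sections and then counts what one lost subject would cost.

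**Step 1: 10.8 against 10.5.** The trigger in 10.8 is a device failure and the decision is the surgeon's. The reasons in 10.5 are the end of the trial, the subject's own request, and an exclusion criterion arising before surgery. An intra-operative failure fits none of them. The first reason could be stretched to one procedure, but its natural meaning is that the whole trial stops. Read literally, 10.8 therefore creates an exit that 10.5 does not contain.

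**Step 2: 10.8 against the rest of the protocol.**
- Sections 5.1 and 8.2.2 describe reverting to manual insertion at any point, with no mention of leaving the study.
- The timing rule in 8.2.2 covers insertions that the surgeon stops early, so incomplete use is foreseen within data collection.
- Sections 8.2.3 and 8.2.6 make no exception for converted subjects.
- Section 10.11 expects every enrolled subject to be implanted with the device, and gives no status to one who is converted.

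These sections lean towards keeping the subject in, but none says so. Two readings remain open.

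**Step 3: what is captured on either reading.** The failure must be documented (10.8). The surgeon completes the questionnaire after the procedure (8.2.1). Intra-operative adverse events go to the sponsor (11.2, 11.3). Section 10.4 places the X-ray before closure of the surgical site, although 8.2.4 also allows it post-operatively.

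**Step 4: what is at risk on the literal reading.** Two items remain: adverse events arising after surgery, and case-report-form entry of the impedance and telemetry values. The measurements are standard of care and would usually still be made; the loss is their transfer to the study. Section 11.1 defines an adverse event as occurring in a study subject, so a site that regards the subject as having left has little reason to report.

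**Step 5: size per subject.**
- Scheduled telemetry assessments (8.2.3): activation + 1 month + 3 months + 6 months = 4.
- Time from surgery to the last one: activation at about 0.5 to 1 month, plus 6 months, gives 0.5 + 6 = 6.5 to 1 + 6 = 7 months.
- Reading that span as the adverse event period is an assumption. Section 8.2.3 schedules telemetry only, and 8.2.6 gives no end date per subject.
- Share of the sample at the maximum enrolment in 9.1: 1/30 = 3.3%, and more if fewer are enrolled.
- If m of 30 subjects have unknown later outcomes and x of the others have a later adverse event, the proportion lies between x/30 and (x + m)/30. The width is m/30, or 3.3 percentage points for each subject lost.

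The protocol gives no failure or conversion rate, so m is unknown and no total follows.

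**The case against.** The strongest reply is that 10.8 is not a withdrawal rule. It sits under a heading about device replacement, in a list of choices made in theatre, and the option ends with completing the implant procedure. Withdrawal has its own section, and the absence of a surgeon's decision from 10.5 can be taken as evidence that 10.8 was never meant to remove anyone. Sections 5.1 and 8.2.2 treat reversion as ordinary conduct within the procedure. This makes loose wording a plausible explanation. It does not remove the problem: the words as written describe leaving the study, no section says that the subject stays, and up to three sites could read the rule differently.

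It can also be said that the deviation log in 10.7 covers omitted visits. It may, but a site that takes 10.8 as permission to stop need not see later omissions as deviations, and a log entry does not replace the data.

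Two limits on the point stand. The figure of 3.3% is simply 1/N and says nothing about how likely a loss is. Whether converted subjects count in the safety reporting is partly for the statistical analysis plan, which is not shown, so no fault is found on that score.

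A reader might infer that failures vanish from the device-use result, so that one failure turns 29/30 (96.7%) into 29/29 (100%). The protocol does not support this. The failure is documented, the questionnaire is still due, and no section removes such subjects from a denominator.

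**Conclusion.** The point holds as a conflict in wording with a real consequence for data collection. Section 10.8, read literally, ends participation because the device failed; 10.5 provides no such reason, and 8.2.2, 8.2.3 and 8.2.6 fit poorly with it.

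The exposure is confined to what follows surgery: for each converted subject treated as having left, later adverse event reports and the recording of four telemetry assessments. The span of about 6.5 to 7 months rests on the assumption that adverse event follow-up ends at the last telemetry visit. Each such subject is at least 3.3% of the sample.

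A reader might go further and conclude that the sponsor chose to drop device failures, or that the safety results will look too favourable. The protocol supports neither. Nothing shows intent, and without a failure rate or data on converted subjects the direction of any bias is undetermined. It should still be corrected, because adverse events that go unreported cannot be restored at analysis.

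**What to change.** In Section 10.8, replace the words about abandoning the study with wording about discontinuing use of the study device. The surgeon's freedom to revert to manual insertion stays as it is.

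State that every subject in whom device use was attempted remains in the study for adverse event reporting and the scheduled data collection, unless the subject withdraws. Reconcile 10.8 with 10.5 so that the two sections give the same account of when participation ends. How converted subjects are counted and reported can be left to the statistical analysis plan.

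The cost is a change of protocol wording, a few more case report forms, and possibly a slightly less favourable summary of device use.
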